9 GENERAL STUDY PROCEDURES

Screening

Research Coordinators (RCs) will work in conjunction with the site investigators to identify patients who meet eligibility criteria at their respective site. Candidates will be initially screened either in person or by phone. For eligible candidates who express interest in participating, a Screening and Enrollment Visit will be scheduled (Visit 1). These candidates may be provided a copy of the informed consent along with supplemental materials that illustrate the device to review prior to Visit 1.

Enrollment and Screen Failures

At Visit 1, subject eligibility will be reviewed. Subjects who are still eligible and have provided written informed consent by signing the Informed Consent Form (ICF) will be considered for enrollment. Subjects will be provided a copy of the signed ICF.

Subjects will be considered enrolled in the study when they have completed training, are successfully fitted with a WCD System, the Monitor is connected to the Garment and the System is powered ON. Subjects who are consented but not enrolled per this definition will be classified as screen failures.

Subject Identification Numbers

Each enrolled subject will be assigned a unique subject identification (SID) number. The first three characters of the SID will reflect the study site number (e.g. S01, S02, ..., S10). The Sponsor will inform each site of its designated site number before the site is opened for enrollment. The last two digits will be assigned based on the enrollment sequence (e.g. the first subject enrolled at each site will be assigned 01) and will be separated from the site designation by a hyphen e.g. S01-05 is subject 05 enrolled at site 01. This number will be used on the Case Report Form (CRF) and on the CareStation website data uploads. The Sponsor will not collect Protected Health Information that would allow specific subject identification (e.g. date of birth, name, initials, medical record number) on the CRF or in the WCD system data.

Unscheduled Visits

Unscheduled visits may be necessary due to AEs or other reasons. The Investigator may examine a subject as often as is medically necessary while the subject is enrolled in the study. Assessments performed at unscheduled visits are at the discretion of the Investigator and will be documented in the CRFs.

Phone Calls

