10 STUDY VISIT PROCEDURES

The Schedule of Events is presented in Appendix A. A detailed description of assessments performed at each study visit is presented below.

Visit 1 (Day 0): Screening and Enrollment

The ASSURE System Training Manual provides detailed instructions for WCD fitting, programming, and System power ON. The following process will be followed at Visit 1.

- Review eligibility criteria
- Explain the purpose and conduct of the study visits to the subject, answer the subject's questions, and obtain written informed consent. This consent process can be performed in advance of Visit 1 at the discretion of the site Investigator.
- Provide the subject with a copy of the signed informed consent
- Obtain demographic data
- Collect ICD Baseline Documentation:
 - Perform a full interrogation of the ICD on the Day of enrollment prior to WCD garment fitting.
 - Synchronize the ICD internal clock to the current time and time zone.
 - If current programmed parameters do not include detection as low as 150 bpm, the Sponsor requests that a monitoring zone at 150 bpm be programmed at the approval of the subject's physician. (ICD data will be used to identify WCD Missed Events (False Negative Detections)).
 - Print the ICD report as part of the source documentation. The report shall include the programmed parameters and arrhythmic episode history.
- Obtain abbreviated limited medical history as specified in the Case Report Form (CRF).
- Perform Wearability Assessment as specified in the CRF. If there is any question regarding skin condition e.g. eczema, the site investigator shall use medical judgement to determine if it disqualifies the subject from participating.
- Obtain urine pregnancy test for women of childbearing potential. If positive, subject is ineligible to participate.
- Perform subject training, including overview of study procedures, hands-on assembly and disassembly of the garment and cable assembly, use and care of the

WCD, and review of manuals. Sponsor representative(s) may be available to assist.

- Have the subject complete the BORG Comfort Scale before they are fit with the Garment. This provides a baseline comfort level to which the follow up BORG Scale scores (obtained at Visit 2 after the subject has worn the WCD) can be compared.

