Adverse events (AEs) as defined below will be monitored continuously during the study from the time the subject is considered enrolled through resolution. Subjects will be instructed to report all AEs during the study, and study personnel will interview the subjects regarding new AEs during each weekly phone call follow up. AEs may be reported by the subject, discovered by Investigator questioning, or detected through physical examination or other means at the study exit visit.

Device Usability Survey

A device Usability Survey will be administered at Visit 2.

Definitions

For the purposes of this study, an **AE** is defined as any untoward medical occurrence in a subject during the study that in the opinion of the investigator is at least possibly-related to use of the ASSURE WCD System.

A serious adverse event (SAE) is defined as any adverse event that:

- Leads to death
- Leads to serious deterioration in the health of a subject that:
 - Results in a life-threatening illness or injury, or
 - Results in a permanent impairment of a body structure or a body function, or
 - Requires in inpatient or prolonged hospitalization \geq 24 hours, or
 - Results in medical or surgical intervention to prevent life-threatening illness or injury or permanent impairment to a body structure or function, or
 - Leads to fetal distress, fetal death or a congenital anomaly or birth defect.

Adverse Device Effect (ADE) is an adverse event related to the use of an investigational medical device.

Anticipated Adverse Device Effects (AADE) are those events related to the use of the device that are reasonably expected to occur as a result of the subject's participation in

the study. The following are AADEs based on results from the series of previous feasibility studies listed in Section 6 and the system engineering hazard analysis:

- Mild to moderate skin irritation
- Muscle Strain
- Emotional discomfort e.g. anxiety, uncomfortable or claustrophobic feelings
- Fall Injury
- Bruising
- Pinched Fingers
- Shoulder discomfort
- Skin Infection (bacterial or yeast)
- ICD System Infection

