An **Unanticipated Adverse Device Effect (UADE)** is any serious adverse effect on health or safety or any life-threatening problem or death caused by, or associated with the device, if that effect, problem, or death was not previously identified in nature, severity, or degree of incidence in this protocol; or any other unanticipated serious problem associated with the device that relates to the rights, safety, or welfare of subjects.

All AEs will be assessed by the investigator according to:

- Whether the event is serious (SAE);
- The severity of the event (mild, moderate, severe); and
- The relationship of the event to device use (possibly, probably, or definitely related)
 - Possibly Related There is a reasonable possibility that the AE may have been primarily caused by device use. The AE has a reasonable temporal relationship to the use of the device and follows a known or expected response pattern to device, but alternative etiology is equally or more likely compared to the potential relationship to the use of the device.
 - Probably Related There is a reasonable probability that the AE may have been primarily caused by device use. The AE has a reasonable temporal relationship to the use of the device and follows a known or expected response pattern to device. Note: this definition assumes no

alternative etiology is equally or more likely compared to the potential relationship to the use of the device.

 Definitely Related – The AE has a strong causal relationship to device use. The AE follows a strong temporal relationship to the use of the device, follows a known response pattern to the device, and cannot be reasonably explained by known characteristics of the subject's clinical state or other therapies.

Whenever possible, the Investigator should group signs or symptoms that constitute a single diagnosis under a single AE term (e.g. redness and swelling can be combined under skin irritation).

Baseline conditions e.g. mild eczema, and AEs identified at Visit 1 following enrollment will be documented during the Wearability Assessment. Baseline conditions are not considered adverse events unless the condition worsens because of study device use.

Adverse Event Reporting Procedures

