Schedule Visit 2 and Weekly Calls with Subject	Х			
Review Usage on CareStationRecord explanations for any daily usage less than 22 hours		X	Х	Х
Obtain ICD Report for all new Episodes since Visit 1			Х	X
Adverse Events (at least possibly device-related)	Х	Х	X	Х
Retrieve all WCD System Components			Х	Х
Device Usability Survey			X	Х

⁶ If the subject is withdrawn early, schedule as soon as possible following the time the study device use is stopped.

⁷ Perform before the Garment is fitted at Visit 1, and after the Garment is removed at Visit 2 or the Early Withdrawal Visit.

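### Adverse event monitoring starts only after training, fitting and power-ON, so device-related events during first handling and fitting at Visit 1 are not clearly required to be recorded

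*Protocol*

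**What the plan says.** Protocol 11 (Evaluation of Adverse Events) states that AEs are monitored continuously "from the time the subject is considered enrolled through resolution". Protocol 9 (Enrollment and Screen Failures) fixes that moment: "Subjects will be considered enrolled in the study when they have completed training, are successfully fitted with a WCD System", and in addition "the Monitor is connected to the Garment and the System is powered ON". A consented subject who does not reach that point is a screen failure.

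Protocol 10 (Visit 1) includes "hands-on assembly and disassembly of the garment and cable assembly" in subject training and lists garment fitting after it. Protocol 11 names "Pinched Fingers" among the anticipated device effects, along with bruising, muscle strain, shoulder discomfort and emotional discomfort such as claustrophobic feelings.

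On where to record Visit 1 events, Protocol 11 (Definitions) says that "AEs identified at Visit 1 following enrollment will be documented during the Wearability Assessment". Appendix A, footnote 7, gives the timing of that assessment: "Perform before the Garment is fitted at Visit 1". Protocol 11 (Wearability Assessment) has its Visit 1 findings entered as baseline conditions if the subject is enrolled.

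**The concern.** The interval outside the window is the subject's first exposure to the device, when an inexperienced user assembles it and the garment is put on and adjusted. Several of the sponsor's own anticipated effects could plausibly arise then. Subjects who find the garment intolerable at fitting may also be the ones who never become enrolled.

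Device-related AEs are a secondary endpoint (Protocol 8), and the study is meant to support a premarket application (Protocol 6). A safety summary whose collection rule omits first handling and fitting, or that different sites apply differently, describes tolerability less completely than it appears to. The recording instruction carries a further risk. If a site repeats the Wearability Assessment after fitting in order to comply, a fitting bruise could be entered as a baseline condition, which Protocol 11 does not count as an AE unless it worsens because of device use.

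**Working it through.** No arithmetic produces this point. It follows from setting the sections side by side.

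1. **Where the window opens.** AE monitoring starts at enrolment (Protocol 11). Enrolment requires completed training, successful fitting, Monitor connection and power-ON (Protocol 9). Training and initial fitting are conditions of enrolment, so they precede it whatever order a site follows within the visit. The tablet check of fit, listed after device set-up in Protocol 10, can fall inside the window.

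2. **Whether other text widens it, for subjects who enrol.**
   - The AE definition (Protocol 11, repeated in SAP 6.1) covers at least possibly related events in the study and has no enrolment limit of its own.
   - Appendix A has an AE entry at Visit 1. This is also consistent with a window that opens late in that visit.
   - The first weekly call is due on Day 7 ± 2, that is Day 5 to Day 9, and asks about the previous week. Counting back seven days, a call on Day 7 or earlier reaches Day 0. A call on Day 8 reaches Day 1 (8 − 7), and a call on Day 9 reaches Day 2 (9 − 7), so Visit 1 is then outside the question.
   - The Visit 2 Wearability Assessment treats new findings against the pre-fitting baseline as AEs if possibly related. It reviews upper-body skin and musculoskeletal conditions about 30 days later. It could find a persisting injury but is unlikely to find a healed finger pinch or a passing claustrophobic reaction.

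   Capture is therefore possible but not clearly required.

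3. **Subjects who stop during fitting.** They are screen failures. Subject identification numbers, which the CRF uses, go to enrolled subjects (Protocol 9). The weekly calls and Visit 2 belong to the participation period. With under two hours of use, these subjects are outside the Safety set (Protocol 12, SAP 8.2). Disposition is tabulated for subjects enrolled and completing (Protocol 12, SAP 8.3). The definition and reporting duty for unanticipated adverse device effects do not mention enrolment, so serious unanticipated effects keep a route. For non-serious events, no recording route is stated.

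4. **The recording instruction.** An event after enrolment comes after fitting, and the Visit 1 Wearability Assessment comes before it. The assessment cannot document an event that has not yet happened.

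5. **Size.** At least 130 and at most 135 enrolled subjects pass through the interval, plus an unstated number of fitted screen failures. Protocol 6 gives the only background on AE types:
   - Subjects in the eight earlier studies: 6 + 12 + 50 + 10 + 117 + 12 + 20 + 32 = 259.
   - AEs: 2 + 6 + 1 + 0 + 9 + 0 + 1 + 8 = 27.
   - Of these 27, 26 were skin irritation and 1 was scratches from a garment seam.

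   None is described as a pinch, strain, bruise or claustrophobic reaction, but the AE windows of those studies are not stated. They neither supply a rate for fitting-time events nor show that it is zero.

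**The case against.** A reader might infer that fitting injuries go unreported altogether, or that pinched fingers are excluded from the safety data. The documents do not support either reading. For subjects who enrol, the AE definition has no enrolment limit, and SAP 4.5 and 6.1 summarise and record AEs over the whole study without filtering on enrolment time. Protocol 11 lists onset and resolution dates for each AE and no clock time, so a fitting injury would carry the same Day 0 date as one just after power-ON. Pinched fingers are listed for device use in general, and subjects swap two garments for washing over about 30 days (Protocol 7), all within the window. Discomfort that continues into wear is also within it.

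Training and fitting take place at a site visit, so the interval is not unobserved. Safety analysis is descriptive. The CRF itself is not available for review and may already provide a place for Visit 1 events.

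All of this stands, and it narrows the point. It leaves three things unanswered: the sentence governing when AE monitoring starts, the missing route for non-serious events in fitted screen failures, and the order of the Wearability Assessment.

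**Conclusion.** The point holds in this form. For enrolled subjects, the text is ambiguous about events during first handling and fitting: recording is neither clearly required nor ruled out. For consented subjects who stop during fitting, no route is stated for non-serious events. The instruction to document post-enrolment Visit 1 AEs in the Wearability Assessment cannot be followed in the listed order.

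The number of events affected cannot be estimated, because the documents give no rate for fitting-time events. The earlier studies suggest no large problem but do not settle it. The conclusion does not depend on a rate. It assumes that the CRF and Training Manual do not already resolve the matter. The effect is confined to the descriptive safety summary, and the primary endpoint, its test and the sample size are untouched. The change is worth making because the inconsistency is plain in the text and inexpensive to remove.

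**What to change.** Reconcile Protocol 9, Protocol 11 (Evaluation of Adverse Events and Definitions) and Appendix A on data capture:

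- Start AE collection at the consented subject's first contact with any WCD component at Visit 1, that is, at the start of hands-on training or fitting.
- Record Visit 1 AEs on the AE form, so that the pre-fitting Wearability Assessment holds baseline conditions only.
- List AEs in consented, non-enrolled subjects separately, with an identifier that does not depend on the enrolment number.

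The enrolment definition and the ITT, PP and Safety sets stay as they are. AEs in non-enrolled subjects would therefore appear in the listing and not in the Safety set summary, and the report should say so.

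The cost is a few sentences in a protocol amendment and use of the existing AE form by staff already present at Visit 1. The downside is a few extra minor AEs and one short listing.

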The Medical Monitor (an independent physician not participating as a clinical investigator in the clinical study) will review and assess in conjunction with the Sponsor all AEs considered by the investigator to be at least possibly related to the use of the ASSURE WCD System to determine if they are reportable to the FDA as Unanticipated Adverse Device Effects (UADEs) per the definition in Section 11. The Medical Monitor will also review all Serious Adverse Events considered by the investigator to be at least possibly related to the use of the ASSURE WCD System to the ASSURE WCD System to verify relatedness and the Serious classification.

Endpoint Review Committee

An independent panel of board-certified electrophysiologists (physicians not participating as clinical investigators in the clinical study) will review all episodes recorded by the ASSURE WCD and/or the subject's ICD in accordance with the *Endpoint Review Committee (ERC) Charter for ASSURE WCD Clinical Evaluation - Detection and Safety Study (ACE-DETECT)* (3334131). These annotations will then be used in the statistical analysis to classify the episodes to calculate the study outcome measures.

Replacements

Subjects who are withdrawn from the study will not be replaced.

Sponsor or Regulatory Agency Termination of the Study

Although the Sponsor intends to complete the study, the right is reserved to discontinue the study at any time for clinical or administrative reasons, or if required by the local regulatory authority.

End of Study

The end of study will be defined as the date of the last visit of the last subject. A summary of the End of Study report will be sent to relevant regulatory authorities and Institutional Review Boards (IRBs) within 6 months of the end of the study.

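### Every relatedness grade needs a known or (for the two lower grades) expected response pattern, so read literally a wholly novel device effect is not an AE and misses the Medical Monitor's UADE review

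*Protocol*

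**What the plan says.** Protocol section 11 (Definitions) makes AE status depend on relatedness. For the study device, an AE is "any untoward medical occurrence in a subject during the study that in the opinion of the investigator is at least possibly-related to use". An SAE is an AE that meets a seriousness criterion, so it passes through the same gate.

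The relationship is then graded possibly, probably or definitely; there is no grade for unrelated events. For Possibly Related, the event must have reasonable timing and must be one that "follows a known or expected response pattern to device, but alternative etiology is equally or more likely compared to the potential relationship" with device use. Probably Related keeps the pattern condition and excludes a rival cause: the event "follows a known or expected response pattern to device. Note: this definition assumes no" equally or more likely alternative. Definitely Related asks for an event that "follows a known response pattern to the device, and cannot be reasonably explained by known characteristics of the subject's clinical state" or by other treatment.

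The UADE definition in the same section covers serious effects linked to the device, subject to this test of novelty: "if that effect, problem, or death was not previously identified in nature, severity, or degree of incidence in this protocol". Under Protocol section 9 (Medical Monitor), the material reviewed for UADEs is "all AEs considered by the investigator to be at least possibly related to the use of the ASSURE WCD System". SAP section 6.1 repeats the AE definition and has the Medical Monitor look for UADEs among the adverse events.

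**The concern.** The UADE rule exists partly to find harm of a kind nobody foresaw. The grades ask for a recognised or foreseen response before an event can count as even possibly related. A serious, well-timed event of an entirely new kind could therefore be left out of the AE data at the site, before independent review.

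This bears on the secondary safety endpoint, on the UADE summary in Protocol section 12, and on protection of subjects during the study. Protocol section 6 says the study will support a premarket approval application. It also shows how little experience stands behind the word known. In the earlier studies that it lists in cardiac patients, wear lasted 2 or 5 days; the 30-day pilot enrolled 32 people from the general population. Thirty-day wear in patients with low ejection fraction and an ICD is where a new effect might first appear.

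**Working it through.** No arithmetic applies. The check sets the definitions side by side and follows an event through them.

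**Step 1: conditions in each grade (Protocol section 11).**

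| Grade | Timing | Response pattern | Competing cause |
|---|---|---|---|
| Possibly | reasonable | known or expected | an equally or more likely alternative is present |
| Probably | reasonable | known or expected | no such alternative |
| Definitely | strong | known | no reasonable explanation from clinical state or other therapy |

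The conditions are cumulative. A pattern condition appears in 3 of 3 grades; 2 of the 3 accept an expected pattern and 1 accepts only a known one.

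**Step 2: which events can be graded.** Every row assumes reasonable timing and a reasonable possibility of device cause.

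| Event | As written | Pattern clause deleted from Possibly only | Both Possibly clauses changed |
|---|---|---|---|
| 1. On the anticipated-effects list, e.g. bruising | gradable | gradable | gradable |
| 2. Known effect, new only in severity or incidence | gradable | gradable | gradable |
| 3. Not listed, but expected from how the device works | Possibly or Probably | Possibly or Probably | Possibly or Probably |
| 4. Neither known nor expected; equally or more likely alternative | no grade | Possibly | Possibly |
| 5. Neither known nor expected; no such alternative | no grade | no grade | Possibly |

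**Step 3: follow rows 4 and 5 onward.** With no grade, the event is not an AE and so not an SAE. The weekly calls and Visit 2 (section 10) and the Wearability Assessment (section 11) all record an AE only when the investigator finds it at least possibly related. The data collection described under Adverse Event Reporting Procedures is for AEs and SAEs. The Medical Monitor's review (Protocol section 9, SAP 6.1) starts from those records. SAP 8.5 presents the Medical Monitor's overriding judgement as a bias control, but that can only reclassify events already admitted.

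**Step 4: compare with the UADE definition.** The two tests use different yardsticks. UADE novelty is judged against what the protocol has identified; the grade asks what response to the device is known or expected. Row 3 can therefore be graded and, if serious, still be a UADE of a new kind. Rows 4 and 5, if serious, meet the novelty limb of the UADE definition and fail every grade. The word expected does not rescue them: section 11 describes anticipated effects as those reasonably expected, so in this protocol the word sits close to anticipated.

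**Step 5: test the simplest repair.** Deleting only the pattern clause from Possibly rescues row 4 but not row 5. Possibly would still demand a rival cause, and Probably and Definitely would still demand a pattern. Row 5 is the most worrying event, so both clauses of Possibly have to change.

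**The case against.** The best case on the other side has four parts.

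- **The gate is a judgement.** AE status turns on whether an event "in the opinion of the investigator is at least possibly-related to use of the ASSURE WCD System", and Possibly Related opens with "There is a reasonable possibility that the AE may have been primarily caused by device use". The grades are applied to events already called AEs. An investigator who suspects the device could reasonably record the event. This stands as a reason not to call exclusion certain. It does not remove the conflict: the next sentence of the definition gives the criteria for that judgement, and sites that read it differently would capture events differently.
- **Other routes exist.** Section 11 requires the investigator to report UADEs to the IRB and gives the sponsor continuing safety evaluation and notification duties. None of these names a grade. The second limb of the UADE definition covers other unanticipated serious problems. Call responses, withdrawal reasons and dates of death are also recorded. This stands, but section 9 gives the UADE determination to the Medical Monitor with the sponsor, on gated events, and no AE record is specified for an event outside the gate.
- **The affected class is small.** The list of anticipated effects has nine entries and is broad, including falls, anxiety and infection of the ICD system. Shock and shock alarms are disabled. This stands.
- **The stakes are limited.** Secondary endpoints are exploratory, and no formal testing of AEs is planned (SAP 4.5 and 5.2). This stands for inference, but not for subject protection or for what a report of no UADEs would mean.

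A reader might go further and infer that all three grades demand a known pattern, that no effect of a new nature can ever be captured, and that a finding of no UADEs is guaranteed by the wording. The documents do not support that. Two grades accept an expected pattern, row 3 events pass, the gate is an opinion, and the reporting duties in section 11 are not tied to a grade.

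**Conclusion.** The definitions conflict and must be reconciled. Read literally, a device effect that is neither known nor expected fits none of the three grades, is not an AE or SAE, and lies outside the Medical Monitor's UADE review, although the UADE definition is written to include it. Listed effects, unlisted but expected effects, and known effects of new severity or incidence are not affected.

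The size cannot be given as a rate, because the documents give no frequency for wholly novel effects. The consequence is qualitative: a report of no UADEs could partly reflect the grading text. The primary endpoint is untouched.

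The conclusion assumes that sites apply the grade wording as criteria and that expected carries roughly its sense in the definition of anticipated effects. The CRF and training text are not in the documents, so whether they repeat or soften the wording is unknown. The change is worth making because it is cheap and the omission concerns subject safety.

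**What to change.** Make two changes to Possibly Related in Protocol section 11:

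1. Delete the condition that the event follow a known or expected response pattern.
2. Reword the alternative-cause clause so that it permits a rival explanation without requiring one, for example: *an alternative etiology may be equally or more likely*.

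Keep reasonable timing and the reasonable possibility of device cause. Keep the pattern condition in Probably and Definitely, where it helps separate those grades from Possibly. Because the reworded Possibly would overlap with the higher grades, state that the highest grade met applies. Any event with reasonable timing and a reasonable possibility of device cause then reaches at least Possibly, including a novel event with no competing cause. If the CRF and site training repeat the current wording, align them.

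The cost is one short protocol edit and matching guidance. A few more events may be graded possibly related, so the reported AE count may look slightly less favourable.
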